3.2. Secondary Efficacy Endpoints

- Proportion of patients achieving serologic clearance of HBsAg on Day 169
- Proportion of patients achieving serologic clearance of HBV DNA on Day 169
- Changes in qHBsAg, HBV DNA, hepatitis B core-related antigen (HBcrAg) and pre-genomic RNA (pg-RNA) levels, Baseline to Days 85 and 169
- Change in IFN-γ frequency by ELISpot assay in PBMCs, Baseline to Days 85 and 169

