2.3.2. Eligibility criteria

2.3.2.1 Inclusion Criteria

- 1. Able and willing to provide informed consent
- 2. Men and women 18 to 65 years of age, inclusive
- 3. Body Mass Index (BMI) 18.0 to 34.9 kg/m², inclusive
- 4. Inactive, treatment-naïve CHB with documented HBsAg positivity for at least 12 months before Day 1. (The history of HBsAg positivity may be reduced to 6 months provided HBV anti-core IgM antibodies are negative).
- 5. qHBsAg ≥ 10 IU/mL but ≤ 200 IU/mL in the 12 months prior to screening or from informed consent to randomization
 - If a patient has more than one qHBsAg value within 12 months and prior to randomization, the patient will be deemed eligible if any one measurement is within the eligible range.
- 6. AST, ALT, INR, albumin, total bilirubin (excluding patients with Gilbert Syndrome, who will only be eligible for study participation if total bilirubin is ≤ 3.0 mg/dL) and direct bilirubin within normal limits at screening. Note: ALT and AST elevations up to 1.5 x ULN are allowed if evidence of hepatic steatosis, defined as one of the following criteria: 1) fatty liver on ultrasound, or other imaging modality or Fibroscan controlled attenuation parameter (CAP) ≥ 260 dB/m. To qualify under these conditions, HBV DNA must be <2,000 IU/mL, and there must be no history or signs of liver disease other than fatty liver and HBV.

- 7. Negative drug screen at screening unless prescribed by a medical practitioner for medical use (NB, recreational and prescription cannabis is allowed)
- 8. For women of childbearing potential (women who are not permanently sterile [documented hysterectomy, bilateral tubal ligation, salpingectomy, or oophorectomy] or postmenopausal [12 months with no menses without an alternative medical cause]):
 - a. Negative pregnancy test on Day 1
 - b. Willingness to practice a highly effective method of birth control with low user dependency from screening through one menstrual cycle after the last dose of study medication, which include:
 - i. Abstinence
 - ii. Sex only with persons of the same sex
 - iii. Monogamous relationship with vasectomized partner
 - iv. Intrauterine device
 - v. Combined estrogen and progestogen containing hormonal contraception associated with inhibition of ovulation (oral, intravaginal, transdermal)
 - vi. Progestogen-only hormonal contraception associated with inhibition of ovulation (oral, injectable or implantable)

vii. Intrauterine hormone-releasing system

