4.2 Efficacy endpoints

4.2.1 Primary Efficacy Endpoint

The proportion of patients achieving virologic response, defined as a 1.0-log reduction in quantitative HBsAg (qHBsAg) or serologic clearance of HBsAg, Baseline to Day 169.

A patient is considered to have achieved the virologic response if one of the following occurs:

1.- Log reduction in qHBsAg of at least 1.0, where

Log reduction = log₁₀ (A/B), where A= qHBsAg at Baseline and B= qHBsAg to Day 169

2.- Serologic clearance of HBsAg is achieved on Day 169:

HBsAg to Day 169 is below the limit of quantitation (defined as 0.05 IU/mL).

Please refer to section 5.3.2 for details on the handling of intercurrent events and missing data.

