4.2.2 Secondary Efficacy Endpoint

Proportion of patients achieving serologic clearance of HBsAg on Day 169

A patient is considered to have achieved serologic clearance of HBsAg on Day 169, if HBsAg on Day 169 is below the limit of quantitation (defined as 0.05 IU/mL).

Proportion of patients achieving serologic clearance of HBV DNA on Day 169

A patient is considered to have achieved serologic clearance of HBV DNA (PCR) on Day 169, if HBV DNA (PCR) on Day 169 is below the limit of quantitation (defined as 10 IU/mL).

Changes in qHBsAg, HBV DNA, HBcrAg and pg-RNA levels, Baseline to Days 85 and 169
 Changes in qHBsAg, HBV DNA, HBcrAg and pg-RNA levels from Baseline to Days 85 and 169
 are defined as:

Change of Test from Baseline to Day 85 = Test value [Day 85] – Test value [Baseline];

Change of Test from Baseline to Day 169 = Test value [Day 169] – Test value [Baseline];

where Test correspond to the following quantitative tests:

qHBsAg, HBV DNA and HBV DNA log, HBcrAg (Log U/mL and kU/mL) and pg-RNA

• Change in LPMIX9 IFN-γ Spot Forming Cells (SFC) by ELISpot assay in PBMCs, Baseline to Days 85 and 169

Change in LPMIX9 IFN-γ SFC by ELISpot assay in PBMCs, Baseline to Days 85 and 169 are defined as:

Change of LPMIX9 IFN-γ SFC from Baseline to Day 85 = LPMIX9 IFN-γ SFC [Day 85] – LPMIX9 IFN-γ SFC [Baseline];

Change of LPMIX9 IFN-γ SFC from Baseline to Day 169 = LPMIX9 IFN-γ SFC [Day 169] – LPMIX9 IFN-γ SFC [Baseline]

Where LPMIX9 is a pool of the 9 peptides contained in FP-02.2. Values for analyses are LPMIX9 raw values corrected with the control.

- Change in LPMIX9 IFN-γ Spot Forming Cells (SFC) by ELISpot assay in PBMCs:
 - Some replicates of some subjects and days, the -ve Control was higher than the analogous LPMIX9 value which led to negative values.
 - Given that the control does not correspond to the analogous LPMIX9 in each of the replicates since the corresponding wells are not linked, the calculation of the continuous parameter to be analyzed, will be revised as follows:
 - Mean (i=1,2,3) of ["Value for Peptide LPMIX9 (R#i)"] Mean (i=1,2,3) of ["-ve Control for Peptide LPMIX9 (R#i)"] where R#i is replicate #i, i=1,2,3
 - Adding a new specification: If the result turns out negative, it will round up to "0"

Please refer to section 5.3.2 for details on the handling of intercurrent events and missing data or all the secondary endpoints.

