This proportion will be compared between treatment groups using Chi-Squared Test or Fisher's Exact Test at a 0.05% two-sided level of significance. Fisher's Exact Test will be used if the expected values of at least the 80% of the cells in the contingency table created for estimating proportions are lower than 5.

This proportion will be analyzed using logistic regression models with treatment group and baseline HBV DNA levels as covariate. The analysis of maximum likelihood and odds ratio estimates for patients predicting a 'Yes' in achieving serologic clearance of HBV DNA on Day 169 will be shown.

5.3.2.2.3 Changes in qHBsAg, HBV DNA, HBcrAg and pg-RNA levels, Baseline to Days 85 and 169

Changes from baseline to days 85 and 169 in qHBsAg, HBV DNA (and HBV DNA log), HBcrAg (Log U/mL and kU/mL) and pg-RNA will be summarized by means of descriptive statistics including mean, standard deviation, median, Q1 and Q3, minimum and maximum by treatment arm.

Changes from baseline for qHBsAg levels will be analyzed fitting a mixed model for repeated measures (MMRM) including treatment group, visits days (Day 1 through Day 169), and baseline values as a covariate. Interactions between visit days and treatment group will also be included. The model will employ an unstructured within patient covariance matrix and a restricted maximum likelihood (ReML) estimation method. In addition, HBV DNA, HBcrAg and pg-RNA will be analyzed in the same manner. The data distribution will be tested for normality and appropriate transformations will be applied, as needed. Any transformation, if applied, will be reported.

Change from baseline is calculated only for patients with non-missing values for both the baseline and the time-point of interest and will be missing otherwise.

5.3.2.2.4 Change in IFN-γ frequency by ELISpot assay in PBMCs, Baseline to Days 85 and 169

Changes from Day 1 to days 85 and 169 in IFN-γ frequency by ELISpot assay in PBMCs (including LPMIX9 IFN-γ SFC and will be summarized by means of descriptive statistics including mean, standard deviation, median, Q1 and Q3, minimum and maximum by treatment arm.

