5.3.8 Data Handling Conventions and Transformations

For HBV serology parameters and viral markers that are continuous in nature as well as HBV pregenomic RNA, the following lower limit of quantitation (LLOQ) have been identified:

Test	LLOQ
HbsAg (IU/mL)	0.05
anti-HBs (mIU/mL)	5.00
quantitative HBV DNA(IU/ml)	10
HbcrAg (Log U/mL)	3
HbcrAg (kU/mL)	1
pg-RNA (log U/mL)	0.49

Also, some of the laboratory parameters could be reported in the form "< x" being "x" the LLOQ for that parameter.

For analyses, the values assigned to the lower limit of quantitation will be imputed as follows:

A value that is 1 unit less than the LLOQ will be used in statistical analyses if the datum is reported in the form of "< x" (where x is considered the LLOQ). For example, if the values are reported as < 50 and < 5.0, values of 49 and 4.9, respectively, will be used in statistical analyses.

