7. APPENDIXES

Appendix 1.- Tables, Figures, and Listings

Appendix 1.- Index of Tables, Figures, and Listings

TFL Number	Title	Analysis Set	Included in	TOP LINE
			Final report	TABLES
Table Number				
14.1 Demograph	ic Data Summary Tables			
14.1.1 Patient Di	sposition			
14.1.1.1	Patient Enrollment and Disposition	All Screened Patients	Yes	V
14.1.1.2	Patient Study Status	All Screened Patients	Yes	
14.1.1.3	Analysis Populations	Randomized Patients	Yes	
14.1.1.4	Protocol Deviations	mITT Population	Yes	
14.1.2 Demograp	phic and Baseline Characteristics			
14.1.2.1	Demographic Characteristics	mITT Population	Only mITT	V
14.1.2.2	Baseline Characteristics	mITT Population	Only mITT	V
14.1.2.3	Specific Disease Characteristics: Fibroscan,	mITT Population	Only mITT	
	Hepatitis B genotype, HCV, HDV and HIV tests			
	and HBV serology and viral markers			
14.1.2.4	Medical History by System Organ Class and	mITT Population	Yes	
	Preferred Term			
14.1.2.5	Baseline Physical Examination	mITT Population	Yes	
14.1.3 Prior and	Concomitant Medications			,
14.1.3.1	Prior Medication by ATC 1st and 2nd level	Safety Population	Yes	
14.1.3.2	Concomitant Medication by ATC 1st and 2nd level	Safety Population	Yes	
14.1.4 Extent of	Exposure for Investigational Products		'	1
14.1.4.1	Treatment Exposure	Safety Population	Yes	
14.2 Efficacy Da	ta Summary Tables and Figures		'	•

TFL Number	Title	Analysis Set	Included in	TOP LINE
			Final report	TABLES
14.2.1 Primary	Efficacy Endpoint			 
14.2.1.1	Summary of patients achieving Virologic Response	mITT Population	Only mITT	V
	on Day 169			
14.2.1.2	Logistic Regression Analysis for Virologic	mITT Population	Only mITT	V
	Response on Day 169			
14.2.2 Seconda	ry Efficacy Endpoint		•	,
14.2.2.1.1	Summary of patients achieving Serologic	mITT Population	Yes	
	Clearance of HBsAg on Day 169			
14.2.2.1.2	Logistic Regression Analysis for Serologic	mITT Population	Yes	V
	Clearance of HBsAg on Day 169			
14.2.2.2.1	Summary of patients achieving Serologic	mITT Population	Yes	
	Clearance of HBV DNA on Day 169			
14.2.2.2.2	Logistic Regression Analysis for Serologic	mITT Population	Yes	V
	Clearance of HBV DNA on Day 169			
14.2.2.3.1	Summary and change from baseline of qHBsAg,	mITT Population	Yes	
	HBV DNA, HBcrAg and pg-RNA levels: Days 85			
	and 169			
14.2.2.3.2	Repeated Measured Mixed Model for qHBsAg,	mITT Population	Yes	
	HBV DNA, HBcrAg and pg-RNA levels: Days 85			
	and 169			

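### HBV DNA clearance counts patients already below 10 IU/mL at baseline, and qHBsAg change has no named log scale: two optional, low-cost additions to the secondary analyses

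*SAP*

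**What the plan says.** **HBV DNA clearance.** Protocol section 3.2 lists the endpoint as "Proportion of patients achieving serologic clearance of HBV DNA on Day 169". SAP 4.2.2 counts a patient as cleared "if HBV DNA (PCR) on Day 169 is below the limit of quantitation (defined as 10 IU/mL". SAP 5.3.2.2.2 divides by all patients in the arm and compares the proportions by chi-square or Fisher's test (Table 14.2.2.2.1). It also fits a logistic model with baseline HBV DNA as covariate (Table 14.2.2.2.2, marked as a top-line table). No inclusion, exclusion or mITT rule requires quantifiable HBV DNA at baseline. The only HBV DNA limit for entry is an upper one, 2,000 IU/mL, under the steatosis allowance.

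**qHBsAg change.** SAP 4.2.2 defines change as the later test value minus the baseline value, for "qHBsAg, HBV DNA and HBV DNA log, HBcrAg (Log U/mL and kU/mL) and pg-RNA". The LLOQ table in SAP 5.3.8 gives pg-RNA in log units and HBsAg only in IU/mL. By contrast, the primary endpoint in SAP 4.2.1 uses "Log reduction in qHBsAg of at least 1.0", and the sample size rests on a 1.3-log mean fall. For the mixed model, SAP 5.3.2.2.3 says "The data distribution will be tested for normality and appropriate transformations will be applied, as needed". For results below the limit, SAP 5.3.8 says "A value that is 1 unit less than the LLOQ will be used in statistical analyses".

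**The concern.** A patient with HBV DNA below 10 IU/mL throughout is reported as having achieved clearance. If such patients are not rare, both crude rates rise, the difference between arms shrinks, and much of the placebo rate reflects patients who had nothing to clear. The protocol's population rationale describes relatively low circulating HBV DNA, so such patients are plausible. Their number is not given.

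For qHBsAg, a plain IU/mL difference scores the same proportional response very differently according to the starting level. The planned route to another scale is a normality check with no test, transformation or fallback named for qHBsAg, so the scale of "Repeated Measured Mixed Model for qHBsAg" (Table 14.2.2.3.2) is settled only after the data are seen.

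**Working it through.** **The plan's own figure.** The documents give power only for the primary endpoint. With 3% v 25%, 40 per arm and two-sided 0.05, exact enumeration of Fisher's test gives 78.0% and the pooled normal approximation 82.2%, so the stated figure of about 80% reproduces. Nothing below changes it.

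**HBV DNA clearance.** From the plan: 40 per arm, two-sided 0.05. Assumed: share u below 10 IU/mL at baseline; clearance of 35% (HepTcell) v 5% (placebo) among the others; 90% of those already below stay below. The chi-square test is used because the SAP turns to Fisher only when at least 80% of the cells have expected counts under 5. In a 2×2 table that means all four cells, which is impossible when the four expected counts sum to 80.

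- Crude rate = 0.9u + (1−u)c, with c = 0.35 or 0.05.
- Difference = 0.30(1−u).
- Share of placebo clearances already below 10 at baseline = 0.9u / [0.9u + 0.05(1−u)].
- Example, u = 10%: 0.09 + 0.9×0.35 = 40.5%; 0.09 + 0.9×0.05 = 13.5%; difference 27.0 points; placebo share 0.09/0.135 = 67%.
- Restricted n per arm = 40(1−u), rounded and held fixed. Letting it vary would lower the restricted power somewhat.

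| u | Crude rates | Difference (points) | Power, all | Power, restricted (n per arm) | Logistic, log / raw covariate | Placebo share |
|---|---|---|---|---|---|---|
| 0 | 35.0% v 5.0% | 30.0 | 96% | 96% (40) | 96% / 96% | 0% |
| 2% | 36.1% v 6.7% | 29.4 | 93% | 95% (39) | 93% / 93% | 27% |
| 10% | 40.5% v 13.5% | 27.0 | 80% | 93% (36) | 84% / 82% | 67% |
| 30% | 51.5% v 30.5% | 21.0 | 49% | 86% (28) | 60% / 53% | 89% |

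The logistic column is simulated with quantifiable HBV DNA assumed log-uniform on 10–2,000 IU/mL.

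**qHBsAg, arithmetic without assumptions about effect.**

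- A 1-log fall scores 1 − 10 = −9 from 10 IU/mL and 20 − 200 = −180 from 200 IU/mL.
- HBsAg loss from 10 IU/mL, set to 0.04, scores −9.96. A 5% fall from 200 scores 190 − 200 = −10.
- On log10 the same two patients score log10(0.04/10) = −2.40 and log10(190/200) = −0.02.
- The substituted value matters. Read literally, one unit less than 0.05 is −0.95, which has no logarithm. The SAP's examples (<50 becomes 49, <5.0 becomes 4.9) imply 0.04.

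**qHBsAg, power.** Single-visit ANCOVA as a stand-in for the mixed model, 40 per arm, baseline assumed log-uniform on 10–200 IU/mL:

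| Assumed scenario | Raw | Log10 |
|---|---|---|
| 25% v 3% responders, 1.2-log fall, SD 0.10 | 47% | 83% |
| Same, SD 0.25 | 21% | 70% |
| 0.15-log shift in all patients, SD 0.20 | 70% | 90% |
| Same shift and SD, plus 3% HBsAg loss in each arm set to 0.04 | 64% | 33% |

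The last row reverses the ranking. Losses score between −2.4 log (from 10 IU/mL) and log10(0.04/200) = −3.7 log (from 200), so one or two of them dominate the log10 variance. The 3% borrows the plan's placebo response rate, which is not a clearance rate. With 1.5% per arm the figures are 64% v 50%.

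Baseline need not lie within 10–200 IU/mL. Inclusion Criterion 5 covers the case "If a patient has more than one qHBsAg value within 12 months and prior to randomization" and accepts any one value in range. With baseline 5–400 IU/mL and SD 0.20, raw v log10 power is 21% v 76% in the responder mixture and 55% v 90% for the 0.15-log shift (no losses).

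**The normality clause.** The SAP names no test; Shapiro-Wilk is assumed. It rejects raw and accepts log10 in 92%–95% of most uniform-shift trials (40% at a 0.3-log shift with SD 0.10, where both scales have 100% power). In the responder mixture it does so in 0%–3% and nearly always rejects both scales.

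**The case against.** - **The clearance rule follows the protocol.** The protocol defines a Day 169 status, and the SAP implements it faithfully. A reader might infer that the rule favours one arm. The documents do not support that: with randomised arms and equal persistence the effect is dilution. This stands.
- **The adjusted table is the top-line one.** The logistic table is marked top line and the crude table is not. Baseline viral markers are summarised in Table 14.1.2.3 and listed by patient in Listing 16.2.6.1. This softens the point. The model still recovers only part of the loss at u = 10% and 30%, and no listed table shows clearance among patients who had something to clear.
- **The inputs are assumed.** The share u, the 35% v 5% and the 90% do not come from the documents. At u = 0 there is no effect, and at 2% the chi-square loss is 2 points. This stands, and is why a count by arm is part of the fix.
- **The SAP already provides for transformation.** It requires a check and the reporting of any transformation, and under a uniform shift that usually leads to log10. The minority-response case, where it fails, is what the log-based primary endpoint measures. This largely stands. What remains is that no scale is named in advance.
- **Log10 is not always better.** A reader might infer that log10 should replace the planned analysis because it is more powerful. The reversal with a few HBsAg losses rules that out, and the population rationale expects losses at low HBsAg.
- **The study is over.** SAP section 2 reports that the Week 24 analysis was done, the endpoints were not met and the study was terminated. Any change is therefore post hoc and affects interpretation only.

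**Conclusion.** Both points hold as optional improvements to unadjusted secondary endpoints in an exploratory Phase 2 trial. Sample size and the primary analysis are untouched.

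The HBV DNA point is the main one. As written, the crude proportion labels unchanged patients as cleared. The cost runs from nothing (u = 0) through 13 points of power (u = 10%) to 37 points (u = 30%), under the assumed 35% v 5% and 90% persistence. The true u is not in the documents.

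The qHBsAg point is one of consistency: it is the only one of the four markers with no log version for the change endpoint, in a trial whose primary response and sample size are on the log scale. It is not a general power argument.

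A reader might also infer that these choices explain why the secondary endpoints were not met. The documents give neither u, nor the qHBsAg scale finally used, nor the results, so that cannot be concluded.

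**What to change.** 1. Keep Table 14.2.2.2.1. Beside it, give the HBV DNA clearance proportion and its test among patients with baseline HBV DNA of 10 IU/mL or more, and report by arm how many were below 10 IU/mL at baseline.
2. Keep Table 14.2.2.3.2. Beside it, add a named mixed model for log10(Day x) minus log10(baseline) qHBsAg, with log10 baseline as covariate.
3. State the value used for HBsAg results below 0.05 IU/mL. The SAP's examples imply 0.04; the sentence itself should say so.
4. Add a rank-based comparison of the log10 change. The SAP already uses the Wilcoxon-Mann-Whitney test for the ELISpot endpoint. It depends little on the substituted value, but it gives little weight to the size of a minority response, so it is a check and not a replacement.
5. Label all of this post hoc, because the Week 24 result is known.

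The cost is SAP wording, two derived variables from data already collected, and outputs beyond the addendum's list. The downsides are a smaller clearance denominator (36 per arm at u = 10%, 28 at u = 30%) and a log10 result that is sensitive to the below-limit substitution.

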4.3 Safety Endpoints

- Incidence and severity of AEs, medically-attended AEs (MAEs), new-onset chronic illnesses (NCIs), and immune-mediated medical conditions (IMCs)
 - An MAE is an AE resulting in hospitalization, emergency room visit, or visit to or from medical personnel (other than routine health care visits).
 - An NCI is an AE that is new (i.e., not present at baseline) and typically chronic. Because of the significance of this designation for the patient's health and for evaluation of vaccine safety, NCIs are expected to be diagnoses, not symptoms, and the Investigator should record sufficient data in the source document to support the diagnosis.
 - An IMCs is any AE appearing in the list of AEs detailed in Appendix 2 of the protocol. Any AE
 assessed by the Investigator as immune-mediated but not appearing in the list will also be
 reported as an IMC.
- Incidence and severity of local and systemic reactogenicity events
 Reactogenicity local or systemic events, and oral temperature will be recorded by the patient in a diary daily for 7 days after each dose. Events will be graded according to the FDA Guidance for

Industry: Toxicity Grading Scale for Healthy Adult and Adolescent Volunteers Enrolled in Preventive Vaccine Clinical Trials [United States Food and Drug Administration 2007].

Reactogenicity events will be categorized separately from AEs unless they are assessed as serious, in which case they will be reported as SAEs. The solicited reactogenicity events are the following:

Local (injection site) reactogenicity events:

- Pain at injection site (without pressure)
- Redness
- Swelling or hardening
- Tenderness

Systemic reactogenicity events

- Fatigue
- Fever
- Chills
- Headache
- Muscle aches
- Joint aches
- Nausea
- Vomiting
- Diarrhoea

Unsolicited events reported by the patients outside of this 7-day reporting period will be recorded as AEs.

Incidence and duration of hepatitis flares;

Hepatitis flares are defined as alanine aminotransferase (ALT) \geq 3 × upper limit of normal (ULN) and > 100 U/L.

The incidence and duration of hepatitis flares will be estimated considering ALT values across all measurements taken (scheduled and repeated) during the treatment period, as follows:

- Incidence of hepatitis flares will be estimated with the number of episodes across measurements on the treatment period per patient.
 - An episode of hepatitis flare will start when the patient experiences ALT $\ge 3 \times ULN$ and > 100 U/L (hepatic flare definition) and will stop in the assessment that verifies one of the following:
 - The definition for hepatitis flare is not verified and there were no missing ALT values in precedent assessments;
 - ii) There is no data for ALT with subsequent assessments without data either (if the patient is still in the study);
 - iii) EOT visit (if the patient ended the study for any reason) and criteria for hepatitis flares were meet until EOT;
 - iv) There is no data for ALT in one or more consecutive visits but there is available data in a subsequent assessment:
 - a. If the definition of hepatitis flare is verified in the assessment with ALT data available after several without data, the episode will continue until i), ii) or iii) occur.
 - b. If the definition of hepatitis flares is not verified in the assessment with ALT data available after several without data, the episode is considered to have finished in the previous assessment where data is available again.
- The duration of an episode of hepatitis flare will be estimated as the difference, in days, between the serum chemistry sample assessment's dates in which the episode starts and the episode stops (according to the definition above) + 1. i.e.,

Duration of hepatitis flares episode =

Sample assessment Date (episode stops) – Sample assessment Date (episode starts) +1 In case there is no sample assessment date, but the visit was performed, the visit date will be taken.

Illustrative example for visits assessments Ass1 to Ass8 (Assessment including repeated assessments between visits):

ASS1	ASS 2	ASS 3	ASS 4	ASS 5	ASS 6	ASS 7	ASS 8	Start	Stop	Start	Stop
								Episode 1	Episode 1	Episode 2	Episode 2
$\sqrt{}$	Χ	$\sqrt{}$	$\sqrt{}$	X				ASS1	ASS2	ASS3	ASS5
$\sqrt{}$	V	NA	NA	NA				ASS1	ASS3		
	V	NA	NA	$\sqrt{}$	Χ			ASS 1	ASS6		
	$\sqrt{}$	NA	NA	X				ASS 1	ASS4		

 V	V			ASS 1	ASS3	
	(EOT)					

 $\sqrt{\ }$ = Criteria for Hepatitis Flares met

X = Criteria for Hepatitis Flares not met

NA = Not data available (but visit has been performed)

• Changes in ALT, aspartate aminotransferase (AST), alkaline phosphatase (AP), gamma glutamyl transferase (GGT), bilirubin total and direct, international normalized ratio (INR) and other laboratory parameters

Changes from baseline across visits in laboratory parameters.

Safety endpoints that are also measured during the Follow-Up period will be assessed separately for the 24-week Treatment Period and 52-week Follow-Up Period.

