3.4. Safety Endpoints

- Incidence and severity of AEs, medically-attended AEs (MAEs), new-onset chronic illnesses (NCIs), and immune-mediated medical conditions (IMCs)
- Incidence and severity of local and systemic reactogenicity events
- Incidence and duration of hepatitis flares, defined as alanine aminotransferase (ALT) \geq 3 × upper limit of normal (ULN) and \geq 100 U/L
- Changes in ALT, aspartate aminotransferase (AST), alkaline phosphatase (AP), gamma glutamyl transferase (GGT), bilirubin total and direct, international normalized ratio (INR) and other laboratory parameters

Safety endpoints will be assessed separately for the 24-week Treatment Period and 52-week Follow-Up Period.

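### Flare stop dates are set at visits without ALT, or while the flare is still active, and the durations are then summarised as complete

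*SAP*

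**What the plan says.** Protocol 3.4 lists "Incidence and duration of hepatitis flares" among the safety endpoints. Protocol 3.4 and SAP 4.3 both ask for the treatment and follow-up periods to be assessed separately. SAP 4.3 derives flares from scheduled and repeated ALT values in the treatment period, and takes duration as stop date minus start date plus one. The stop rules are:

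- **Rule i**: "The definition for hepatitis flare is not verified and there were no missing ALT values in precedent assessments". The episode stops at the first value that no longer meets the definition.
- **Rule ii**: "There is no data for ALT with subsequent assessments without data either (if the patient is still in the study"). In row 2 of the SAP's example table (met, met, NA, NA, NA) the stop is ASS3, the first visit without ALT.
- **Rule iii**: "EOT visit (if the patient ended the study for any reason) and criteria for hepatitis flares were meet until EOT". In row 5 (met, met, met at EOT) the stop is the EOT visit.
- **Rule iv-a**, a gap followed by a value that meets the definition: "the episode will continue until i), ii) or iii) occur". Row 3 is one episode, ASS1 to ASS6.
- **Rule iv-b**, a gap followed by a value that does not meet it: "the episode is considered to have finished in the previous assessment where data is available again". In row 4 (met, met, NA, NA, not met) the stop is ASS4.

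The table's key reads "NA = Not data available (but visit has been performed"), and the text adds "In case there is no sample assessment date, but the visit was performed, the visit date will be taken". A visit with no ALT result can therefore supply the stop date.

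SAP 5.3.3.8 summarises each patient's maximum and average duration with the usual descriptive statistics. Neither section flags, censors or counts episodes that were never seen to resolve.

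**The concern.** Under rule i the stop date rests on an ALT value showing that the flare definition is no longer met. Under rules ii and iv-b it rests on a visit with no ALT value, and under rule iii on a value that still meets the definition. All four kinds of episode then enter the same mean, median and maximum.

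This also departs from the SAP's general practice. Section 5.3.9.1 bases continuous summaries on observed data and plans no imputation of AE resolution dates, and section 5.3.3.12 does not impute missing laboratory data. Section 4.3 gives no reason for the exception.

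At stake is a protocol safety endpoint: a flare last seen active would be read as having a known, finished length. There is also a gap in coverage. Rule iii is limited to patients who ended the study, and the flare derivation to the treatment period. No rule clearly covers a patient in flare at Day 169 who enters follow-up, although Protocol Table 2 schedules liver panels at Days 232, 323, 414 and 505.

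**Working it through.** **1. Reproducing the SAP's example.** Coding rules i to iv and applying them to the five example patterns returns the SAP's start and stop assessments in every row. ASS1 was taken as meeting the definition where the extracted cell is blank, since the table starts those episodes at ASS1.

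**2. Days.** Spacing is an assumption: the SAP does not date the example assessments, and they include repeats. Two values are shown: s = 28 days (dosing visits) and s = 7 days (the weekly liver monitoring in Protocol 4.1). Duration is (number of intervals × s) + 1, counted from the first value meeting the definition.

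| Pattern | Stop | Formula | s = 28 | s = 7 |
|---|---|---|---|---|
| Row 4, last value meeting definition | ASS2 | s + 1 | 29 | 8 |
| Row 4, SAP (iv-b) | ASS4 | 3s + 1 | 85 | 22 |
| Row 4, first observed value not meeting it | ASS5 | 4s + 1 | 113 | 29 |
| Row 2, last value meeting definition | ASS2 | s + 1 | 29 | 8 |
| Row 2, SAP (ii) | ASS3 | 2s + 1 | 57 | 15 |
| Row 5, SAP (iii), lower bound only | ASS3 (EOT) | 2s + 1 | 57 | 15 |

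Row 2 has no upper bound. Rule iv-b stops exactly one assessment before the stop that rule i's convention would give.

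**3. Direction.** Each missing ALT was filled in both ways, and the first-episode stop under rule i on the completed data was compared with the SAP's stop.

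- **Rule iii**: the definition is met at EOT, so the rule i stop must come later. Always understated.
- **Rule ii (row 2)**: of eight completions, four stop at ASS3, two at ASS4, and two reach ASS5 (one of these still active). The SAP assigns ASS3. Equal or understated.
- **Rule iv-b, one missing visit** (met, met, NA, not met): the stop is ASS3 or ASS4; the SAP assigns ASS3. Equal or understated.
- **Rule iv-b, two missing visits (row 4)**: of four completions, two stop at ASS3, one at ASS4 and one at ASS5. The SAP assigns ASS4. Too long by one interval, right, or too short by one.
- **Rule iv-a (row 3)**: one of four completions is a single episode to ASS6; the other three are two shorter episodes. Equal or overstated, with the episode count reduced where two are merged.

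These are counts of possible patterns, not probabilities.

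**4. Simulation.** Assumptions: visits every 28 days from Day 1 to Day 169, onset uniform over that span, exponential flare length with mean 28, 56 or 84 days, and 10% or 30% of ALT values missing at random. Every patient in flare at Day 169 was closed under rule iii. Recorded duration of the first episode was compared with the true flare length, including time before the first qualifying value. Ranges are over the six scenarios.

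| Closing rule | Mean recorded (days) | Mean true (days) | Recorded too short |
|---|---|---|---|
| i (including episodes carried over a gap by iv-a) | 36.9–52.2 | 33.9–51.5 | 33–50% |
| ii | 40.4–65.0 | 54.2–134.8 | 58–87% |
| iii | 13.5–43.5 | 55.5–141.8 | about 100% |
| iv-b | 39.4–50.9 | 39.8–58.9 | 45–63% |

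For iv-b, one scenario was longer than the truth on average (43.0 against 40.5). Over all first episodes the means were 32.8–48.5 recorded against 40.5–103.5 true. That overall gap leans heavily on closing every flare at Day 169 under rule iii, which the SAP does only for patients who ended the study.

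**The case against.** A reader might infer that missing ALT generally shortens recorded durations. The rules do not support that. Rule iv-b places the stop between the last value meeting the definition and the first one not meeting it; 113 days in row 4 is the top of that interval, not the truth. Rule iv-a can only lengthen an episode. This objection stands, and it limits the claim of understatement to rule iii and, against rule i, rule ii.

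A reader might also infer that the comparison between arms is biased, or that these flares are reported as resolved. Neither follows. Duration is summarised descriptively with no planned test, nothing in the documents shows missingness differing by arm, and the SAP defines no resolved or unresolved status. What stands is that the summary does not distinguish the two kinds of episode.

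The practical effect may be small. Repeated assessments count, and weekly panels apply at ALT or AST of 5 × ULN or more, so gaps may be much shorter than 28 days; flares between 3 and 5 × ULN do not trigger weekly panels on ALT alone. Phase 1 saw no flares (Protocol 1.3), SAP section 2 reports no significant safety events at the interim analysis, and Listings 16.2.8.2 and 16.2.10.1 let a reader follow individual courses. This bears on importance, not on whether the rule is right.

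Finally, carrying treatment-period episodes into follow-up data could blur two periods that must be assessed separately. That is a fair constraint on the remedy.

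**Conclusion.** The point holds in a limited form. SAP 4.3 sets stop dates at visits without ALT (rules ii and iv-b) and at EOT with the flare still active (rule iii), and SAP 5.3.3.8 treats the resulting durations as complete. Durations are always understated under rule iii. Under rule ii they are equal or understated relative to rule i. Across gaps the direction is indeterminate: rule iv-b stops one assessment earlier than rule i's convention, and rule iv-a can overstate by merging episodes.

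The day counts depend on assumed spacing. Row 4 gives 85 days within 29 to 113 at 28 days, and 22 within 8 to 29 at 7 days. The simulated means rest on assumed flare lengths and missingness, not trial data, and the documents do not show how many flares fall under each rule. This is a minor but real defect in the derivation of a protocol safety endpoint, together with an unclear case for patients in flare at Day 169 who continue.

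**What to change.** Use one stop convention and mark what is not known:

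- End every episode at the first observed ALT value that does not meet the flare definition, as rule i does.
- Where the treatment period holds no such value, flag the episode as unresolved at the last ALT value meeting the definition. This covers the present rules ii and iii and the patient in flare at Day 169. Keep it in the incidence count, report its duration as right-censored (a lower bound), and give the number of such episodes by arm.
- In the flare listing, show the minimum and maximum possible duration of every episode with a gap.
- Use ALT accrued in follow-up only to give an eventual resolution date in that listing. Keep the treatment-period and follow-up summaries separate, as Protocol 3.4 and SAP 4.3 require.

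The cost is a rewording of the rule and minor reprogramming of Table 14.3.6.1 and Listing 16.2.10.1, with no new data. Some durations will appear as lower bounds, and some of those will be numerically smaller than now: at 28-day spacing, row 2 changes from 57 days to at least 29. The flag and count are therefore needed alongside the figure. Because the study ended early, follow-up ALT will give resolution dates for only some episodes.
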